11. MEASUREMENT OF EFFECT

Therapeutic response will be assessed by serial scans. Overall clinical response rate and tumor progression will be assessed by evaluating nonbiopsied lesions if present, using standard methods (RECIST), including physical exam and CT scans performed before therapy, at 13 weeks (before drug administration), and every subsequent 9 weeks through 1 year and every 12 weeks in year 2 according to standard practice. For cycles with scans scheduled, the scans shall occur before MK-3475 administration. Patients will be managed in accordance with RECIST guidelines as published by Eisenhauer [[Eisenhauer 2009](#)]. However, MK-3475-treated patients who appear to be progressing at the 13-week scan can continue therapy until progression is confirmed at the 17-week scan, provided the patient is otherwise stable.

11.1 Antitumor Effect—Solid Tumors

For the purposes of this study, patients with advanced MCC should be evaluated for response by spiral CT scan in accordance with standard practice at 9-week intervals, with the initial scan at week 13 of the trial, before drug administration. Throughout the trial, for cycles with scans scheduled, scans shall occur before scheduled drug administration so that the investigator may evaluate the patient for possible progression before administering the next dose of study medication. Response and progression will be evaluated in this study using the new international criteria proposed by the revised RECIST guideline (Version 1.1)[[Eisenhauer 2009](#)]. Changes in the largest diameter (unidimensional measurement) of the tumor lesions and the shortest diameter in the case of malignant lymph nodes are used in RECIST.

Immunotherapeutic agents such as MK-3475 may produce antitumor effects by potentiating endogenous cancer-specific immune responses that may be functionally anergic. The response patterns seen with such an approach may extend beyond the typical time course of responses seen with cytotoxic agents and can manifest a clinical response after an initial increase in tumor burden or even the appearance of new lesions. Standard RECIST guidelines may not provide a CR assessment of immunotherapeutic agents such as MK-3475, especially at early therapeutic time points. Because of the possibility that the initial scan at 13 weeks may misclassify MK-3475 responders as progressing on therapy, those MK-3475-treated patients who appear to be progressing at week 13 can continue therapy until progression is confirmed at the 17-week scan, providing they meet the guidelines stated above ([Section 5.1.1](#)). If the patient is found to be progressing on the 17-week scan, the investigator will determine whether to discontinue protocol therapy and begin other systemic therapy, such as cytotoxic chemotherapy, or alternatively to continue MK-3475 treatment. If MK-3475 therapy is discontinued, the patient will attend the end-of-treatment and 30-day follow-up visits. The time of progression will be reported as the first time that progression was noted. If patients regress or have SD as determined by the confirmatory 17-week imaging study, the time of eventual progression will be separately reported.

If progression is noted on subsequent routine disease monitoring scans (≥ 22 weeks), which will continue throughout the trial at 9- or 12-week intervals, a confirmatory scan will be obtained 4 weeks later. If this confirmatory scan identifies an MK-3475-treated patient as progressing on therapy, the investigator will determine whether to discontinue protocol therapy and begin other systemic therapy, such as cytotoxic chemotherapy, and follow patient as indicated above, or

alternatively to continue MK-3475 treatment. (See [Overall Trial Schema](#) and [Patient Visit Timeline](#)).

11.1.1 **Definitions**

Evaluable for Objective Response. All patients that have received at least 1 injection of MK-3475 will be considered evaluable for response.

A patient on MK-3475 who is identified as progressing on therapy at the initial 13-week scan may continue receiving MK-3475 until progression is confirmed by a subsequent scan at 17 weeks. Patients may only receive treatment while waiting for confirmation of PD if the following criteria are met:

- Absence of signs and symptoms (including worsening of laboratory values) indicating disease progression
- No decline in ECOG performance status
- Absence of rapid progression of disease
- Absence of progressive tumor at critical anatomical sites (e.g., cord compression) requiring urgent alternative medical intervention

If these criteria are met, it is advisable to keep patients on MK-3475 until confirmation of progression but is subject to the discretion of the treating physician. Patients that are deemed clinically unstable are not required to have repeat imaging for confirmation.

If progression is confirmed, then the patient will be discontinued from trial treatment. If progression is not confirmed, then the patient should resume/continue trial treatment and have their next scan according to the standard follow-up schedule on week 22 then every 9 weeks thereafter during the first year of treatment and every 12 weeks during the second year of treatment.

Alternatively, if progression is confirmed, patients who are clinically stable will be eligible to receive continued MK-3475. Patients who have not achieved CR (either responding, stable or progressing lesions) may have an optional biopsy of tumor prior to continuing therapy to assess potential reasons for the lack of response to MK-3475. Patients will then continue MK-3475 treatment and scans per the study calendar.

For patients who discontinue trial treatment for reasons other than disease progression, imaging during the post-treatment follow-up period is to continue as described in Section 5.1.1 until confirmed disease progression, start of a new antineoplastic therapy, death or end of study, whichever occurs first.

Local reading (investigator assessment with site radiology reading by RECIST 1.1 criteria) will be used to determine patient eligibility and for patient management. Radiologic images will be collected and stored for a possible retrospective analysis of patient eligibility and treatment response to be performed by a central vendor, including RECIST 1.1.

Evaluable Non-target Disease Response. Patients who have lesions present at baseline that are evaluable but do not meet the definitions of measurable disease, have received at least 1 cycle of therapy, and have had their disease re-evaluated will be considered

evaluative for non–target disease. The response assessment is based on the presence, absence, or unequivocal progression of the lesions.

Patients who do not receive a post-baseline scan due to discontinuing treatment as a result of toxicity should be considered evaluative for response.

11.1.2 *Disease Parameters*

Measurable disease. Measurable lesions are defined as those that can be accurately measured in at least one dimension (longest diameter to be recorded) as ≥ 20 mm by chest x-ray or as ≥ 10 mm with CT scan, magnetic resonance imaging (MRI), or calipers by clinical exam. All tumor measurements must be recorded in millimeters (or decimal fractions of centimeters).

Note: Tumor lesions that are situated in a previously irradiated area or in an area subjected to other locoregional therapy are usually not considered measurable unless there has been demonstrated progression in the lesion.

Malignant lymph nodes. To be considered pathologically enlarged and measurable, a lymph node must be ≥ 15 mm in the short axis when assessed by CT scan (CT scan slice thickness recommended to be no greater than 5 mm). At baseline and in follow-up, only the short axis will be measured and followed.

Nonmeasurable disease. All other lesions (or sites of disease), including small lesions (longest diameter < 10 mm or pathological lymph nodes with ≥ 10 to < 15 mm short axis), are considered nonmeasurable disease. Bone lesions, leptomeningeal disease, ascites, pleural/pericardial effusions, lymphangitis cutis/pulmonitis, inflammatory breast disease, and abdominal masses (not followed by CT or MRI), are considered as nonmeasurable.

Note: Cystic lesions that meet the criteria for radiographically defined simple cysts should not be considered as malignant lesions (neither measurable nor nonmeasurable) since they are, by definition, simple cysts.

“Cystic lesions” thought to represent cystic metastases can be considered as measurable lesions, if they meet the definition of measurability described above. However, if noncystic lesions are present in the same patient, these are preferred for selection as target lesions.

Target lesions. All measurable lesions up to a maximum of 2 lesions per organ and 5 lesions in total, representative of all involved organs, should be identified as **target lesions** and recorded and measured at baseline. Target lesions should be selected on the basis of their size (lesions with the longest diameter), be representative of all involved organs, but in addition should be those that lend themselves to reproducible repeated measurements. It may be the case that, on occasion, the largest lesion does not lend itself to reproducible measurement, in which circumstance the next largest lesion that can be measured reproducibly should be selected. A sum of the diameters (longest for non-nodal lesions, short axis for nodal lesions) for all target lesions will be calculated and reported as the baseline sum diameters. If lymph nodes are to be included in the sum, then only the short axis is added into the sum. The baseline sum diameters will be used as reference to

further characterize any objective tumor regression in the measurable dimension of the disease.

Non-target lesions. All other lesions (or sites of disease) including any measurable lesions over and above the 5 target lesions should be identified as **non-target lesions** and should also be recorded at baseline. Measurements of these lesions are not required, but the presence, absence, or in rare cases unequivocal progression of each should be noted throughout follow-up.

11.1.3 **Methods for Evaluation of Measurable Disease**

In this study, all tumors will be measured using spiral CT scan.

All baseline evaluations should be performed as closely as possible to the beginning of treatment and never more than 4 weeks before the beginning of the treatment.

11.1.4 **Response Criteria**

11.1.4.1 **Evaluation of Target Lesions by RECIST**

Complete Response (CR): Disappearance of all target lesions. Any pathological lymph nodes (whether target or non-target) must have reduction in short axis to <10 mm.

Partial Response (PR): At least a 30% decrease in the sum of the diameters of target lesions, taking as reference the baseline sum diameters.

Progressive Disease (PD): At least a 20% increase in the sum of the diameters of target lesions, taking as reference the smallest sum on study (this includes the baseline sum if that is the smallest on study). In addition to the relative increase of 20%, the sum must also demonstrate an absolute increase of at least 5 mm. (**Note:** the appearance of one or more new lesions is also considered progression).

Stable Disease (SD): Neither sufficient shrinkage to qualify for PR nor sufficient increase to qualify for PD, taking as reference the smallest sum diameters while on study.

11.1.4.2 **Evaluation of Non-Target Lesions by RECIST**

Complete Response (CR): Disappearance of all non-target lesions and normalization of tumor marker level. All lymph nodes must be non-pathological in size (<10 mm short axis).

Note: If tumor markers are initially above the upper normal limit, they must normalize for a patient to be considered in complete clinical response.

Non-CR/Non-PD: Persistence of one or more non-target lesion(s) and/or maintenance of tumor marker level above the normal limits.

Progressive Disease (PD): Appearance of one or more new lesions and/or

unequivocal progression of existing non-target lesions. *Unequivocal progression* should not normally trump target lesion status. It must be representative of overall disease status change, not a single lesion increase.

Although a clear progression of “non-target” lesions only is exceptional, the opinion of the treating physician should prevail in such circumstances, and the progression status should be confirmed at a later time by the review panel (or PI).

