5. TREATMENT PLAN

This is a multi-institution, CITN Cooperative trial of MK-3475 in patients with advanced MCC, who have not received prior systemic therapy for their disease. The trial is open-labeled and nonrandomized. Patients who have not received any previous systemic therapy for their disease will be treated with MK-3475, given every 3 weeks.

ORR, PFS, and DOR will be monitored by CT scans at week 13 and then at 9-week intervals. At 1 year, the scan frequency will be decreased to every 12 weeks. Responses and progression will be assessed by RECIST 1.1 criteria. OS will be chronicled and reported.

Patients who appear to progress on the initial scan, occurring at week 13 of therapy, will be allowed to continue on therapy if otherwise stable, until a confirmatory scan is obtained at 17 weeks. If the 17-week scan confirms progression, the study treatment will be discontinued and the patient will be followed for survival. Alternatively, MK-3475 treatment may be continued in the setting of progressive disease if the patient is otherwise clinically stable as defined by the following criteria:

- Absence of clinical symptoms or signs indicating clinically significant disease progression
- ECOG performance status ≤ 1
- Absence of rapid disease progression or threat to vital organs or critical anatomical sites (e.g., spinal cord compression) requiring urgent alternative medical intervention

Patients who appear to progress on any subsequent scan will be allowed to continue on therapy if otherwise stable, until a confirmatory scan is obtained 4 weeks later. If the scan repeated 4 weeks later confirms progression, the study treatment will be discontinued and the patient will be followed for survival, or alternatively, continue MK-3475 treatment, if patient is otherwise clinically stable as described above.

Therapy after progression is at the discretion of the patient and primary physician.

Patients with stable disease (SD) or partial response (PR) can be treated up to 2 years at patient and investigator discretion. Patients that achieve a complete response (CR) can discontinue treatment after 6 months of therapy provided that patient has had at least 2 cycles past validation of CR. Patients that recur off of therapy will be eligible for retreatment at patient and investigator discretion, provided they meet the criteria for retreatment and the trial is ongoing.

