Note: Patients will receive up to 24 months of trial treatment calculated from the date of first dose. Subjects who stop MK-3475 after 24 months may be eligible for up to 1 year of additional trial treatment if they progress after stopping trial treatment provided they meet the requirements detailed in [Section 5.10](#).

The first radiologic assessment of tumor response status will be performed at Week 13 (as consistent with standard of care). This assessment shall occur before drug administration scheduled for Week 13. However, if a patient is found to be progressing on MK-3475 at this initial scan, the patient can continue on MK-3475 if otherwise stable (see criteria below). A confirmatory scan will be performed at week 17, as immunomodulatory therapies may result in an early increase in lesion size due to influx

of immune cells. This immune activation and infiltration reflects the therapeutic mechanism and, therefore, an early increase in tumor size in this context may herald a therapeutic response rather than progression.

Thus, it is recommended that a patient with an unconfirmed early (<17 weeks) progression should continue therapy with MK-3475 waiting for confirmation of disease progression, but ONLY if the following criteria are met:

- Absence of clinical signs and symptoms (including worsening of laboratory values) indicating clinically significant disease progression
- ECOG performance status ≤ 1
- Absence of rapid disease progression or threat to vital organs or critical anatomical sites (e.g., spinal cord compression) requiring urgent alternative medical intervention

As depicted in the [Overall Trial Schema](#), an MK-3475-treated patient whose progression is confirmed at the 17-week scan will discontinue therapy. Alternatively, if patient is otherwise clinically stable per criteria above, they may be continued on MK-3475 treatment. The next scan will be performed at Week 22 and then every 9 or 12 weeks per the [Patient Visit Timeline](#). MK-3475 will be discontinued if the tumor burden increases by 25% or more following initial confirmation of progression.

In patients without progression and in patients with progression who continue treatment with MK-3475, disease radiologic monitoring should continue to be assessed at 9-week intervals through the first year of treatment and then at 12-week intervals throughout the duration of the study. [Section 5.4](#) describes criteria for discontinuing treatment.

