- i. For women of reproductive potential, a urine pregnancy test should be performed within 72 hours before first dose of trial treatment. If urine pregnancy results cannot be confirmed as negative, a serum pregnancy test performed by the local study site laboratory will be required. Pregnancy tests (serum and/or urine tests) should be repeated if required by local guidelines.
- j. After Cycle 1, lab samples can be collected up to 72 hours before the scheduled time point. See [Section 5.1.1](#) for details regarding laboratory tests.
- k. Urinalysis and thyroid function testing to be repeated every 6 cycles after baseline (cycles 6, 12, 18, etc.) and at the Post-Treatment Follow Up visit.
- l. Unresolved abnormal labs that are drug related AEs should be followed until resolution. Labs do not need to be repeated after the end of treatment if labs are within normal range.
- m. Concomitant medications – Enter new medications started during the trial through the safety follow-up visit. Record all medications taken for SAE reporting as defined in [Section 5.3.1](#).
- n. The initial tumor imaging will be performed within 28 days before the first dose of trial treatment. Scans performed as part of routine clinical management are acceptable for use as the screening scan if they are of diagnostic quality and performed within 28 days before the first dose of trial treatment. On-study imaging will be performed and reviewed at week 13 before drug administration. Patients who show progression at week 13 will continue on therapy and have a conformational scan at week 17. Patients with

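### Sections 5.1.1, 5.8, 11.1.1 and calendar footnote n give conflicting conditions for dosing while a first progression awaits confirmation

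*Combined protocol and SAP*

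**What the plan says.** Five places in the current text bear on treatment between a first progression and its confirmatory scan.

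- **Section 5** says that a patient who appears to progress at week 13 "will be allowed to continue on therapy if otherwise stable", up to the week-17 scan. The criteria list that follows is attached to continuing in the setting of progressive disease once week 17 has confirmed it.
- **Section 5.1.1** recommends that a patient with unconfirmed early progression "should continue therapy with MK-3475 waiting for confirmation of disease progression, but ONLY if the following criteria are met". Its list includes "ECOG performance status ≤ 1" and the absence of signs and symptoms, laboratory worsening among them, of clinically significant progression.
- **Section 5.8** applies one list both before and after confirmation. It has the same ECOG ceiling and the clinically-significant qualifier, and does not mention laboratory values. Its table has clinically unstable patients discontinue at the first radiologic progression.
- **Section 11.1.1** states: "Patients may only receive treatment while waiting for confirmation of PD if the following criteria are met". Its list includes "No decline in ECOG performance status" and "Absence of signs and symptoms (including worsening of laboratory values) indicating disease progression".
- **Study Calendar, footnote n**, which is attached to tumor imaging, states: "Patients who show progression at week 13 will continue on therapy". No stability condition goes with it.

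Section 11.1 refers the reader back to 5.1.1 for the conditions. Section 11.1.1, directly below, then gives a different list.

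**The concern.** A patient can be allowed treatment by one section and barred by another at the same decision. The decision is a safety matter, because it concerns dosing someone whose disease may be progressing. It also affects the data. A site that follows one section can be recorded as deviating from another, so deviations cannot be judged to one standard. The conditions also settle who is still on drug at the confirmatory scan. Section 13.5.1.1 counts patients with confirmed progression as progressed even if they later respond, and Section 11.1 reports separately the eventual progression of patients who regress or are stable at week 17. In a single-arm trial with ORR as primary endpoint, who is on drug at that scan should not depend on which section the site read.

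**Working it through.** No sample size, error rate or event count is involved. The check is a comparison of the lists.

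| Condition | 5.1.1 | 5.8 | 11.1.1 | Footnote n |
|---|---|---|---|---|
| ECOG | 1 or less | 1 or less | no decline, reference visit not stated | none |
| Signs and symptoms | of clinically significant progression | of clinically significant progression | of progression, no qualifier | none |
| Laboratory worsening | counted | not mentioned | counted | none |
| Site of disease | vital organs or critical sites | vital organs or critical sites | critical sites only | none |
| Clinically unstable patient | not among those advised to continue | table: discontinue | not permitted | will continue, read literally |

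The last 11.1.1 list item reads "Absence of progressive tumor at critical anatomical sites (e.g., cord compression) requiring urgent alternative medical intervention"; vital organs are not named.

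**ECOG, decline read against baseline (an assumption).** Section 3.1.4 admits patients at ECOG 0 or 1.

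| Entry to progression | 5.1.1 and 5.8 | 11.1.1 |
|---|---|---|
| 0 to 0 | met | met |
| 0 to 1 | met | **not met** |
| 1 to 1 | met | met |
| 1 to 0 | met | met |
| 0 to 2, or 1 to 2 | not met | not met |

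The lists split on the 0-to-1 patient.

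**ECOG, decline read against the previous visit.** A patient who moved to 1 earlier and has stayed there meets both rules. A patient already at 2 and unchanged meets the 11.1.1 item but fails 5.1.1 and 5.8. The direction of the conflict therefore depends on a reference visit that the protocol does not give.

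**Signs and symptoms.** A patient whose signs indicate progression, but not clinically significant progression, passes this item in 5.1.1 and 5.8 and fails it in 11.1.1. This split needs no assumption about the reference visit. If laboratory worsening is the only sign and it points to clinically significant progression, the patient fails 5.1.1 and 11.1.1, while 5.8 does not address the case.

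**Footnote n against the 5.8 table.** For a clinically unstable week-13 progressor, the footnote says treatment continues and the table says it stops. Read literally, these are opposite instructions.

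**Exposure at stake.** Cycle k starts in week 1 + 3(k − 1). Cycle 5 is week 13, Cycle 6 is week 16 and Cycle 7 is week 19. At most two doses, in weeks 13 and 16, fall between the first scan and the week-17 scan.

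**The case against.** The strongest reply is that the lists differ in strictness and do not truly contradict. Section 5.1.1 recommends continuing, 5.8 permits it at the investigator's discretion, and 11.1.1 also leaves it to the treating physician. A site that stops a 0-to-1 patient breaks no mandatory rule in 5.1.1 or 5.8. That is correct. The opposite case remains, though: a site that doses this patient, as 5.1.1 recommends, breaches the only-if wording of 11.1.1 when decline is read from baseline. The discretion in 11.1.1 begins once its own criteria are met; it does not choose between lists.

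The cross-reference in 11.1 can be read as making 5.1.1 the primary list. It points that way, but it does not cancel the list in 11.1.1.

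Footnote n is an imaging footnote; dosing is in footnote b. Footnote n also says scans precede dosing so that the investigator can check for progression, and other sections state stability conditions. Loose drafting is a fair description. A reader might infer that sites follow the calendar and dose unstable patients, but nothing in the documents shows what sites do.

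A reader might also count the Section 5 list as a further conflicting rule for the wait to week 17. It is not one, because it is attached to continuing despite confirmed progression.

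On the response rate, stopping treatment need not end observation: the 5.8 table keeps a repeat scan where possible and allows a restart if that scan shows no progression. The only late-response figure in the documents is 3.6%, from a melanoma trial (Section 2.4.2). Carried over to 50 patients purely as an assumption, it gives 0.036 × 50 = 1.8, and only patients whose status differs between the lists would be affected.

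Finally, the Study Summary describes all 50 patients as enrolled, so many week-13 decisions may be past. No dates confirm this. Section 5.8 also covers later first progressions, retreatment under 5.10 remains possible, and review of deviations still needs one standard.

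**Conclusion.** The inconsistency is real and lies in current text. For dosing while a first progression awaits confirmation, 5.1.1 and 5.8 conflict with 11.1.1 on ECOG and on the symptom qualifier. Section 5.8 also differs from the other two in leaving out laboratory values, and footnote n drops all conditions. The 0-to-1 example assumes that decline is measured from baseline; the symptom conflict and the footnote conflict do not need that assumption.

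The size cannot be given. The documents contain no ECOG distribution, no count of week-13 progressors and no count of unstable patients, so any percentage of the trial would be a guess. Nor do they support a claim that ORR is biased. There is a route by which it could be affected, but it runs through at most two doses per week-13 progressor and its effect cannot be computed. This should be corrected for patient safety and for consistent treatment and deviation review.

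**What to change.** Reconcile Sections 5, 5.1.1, 5.8 (text and table) and 11.1.1 and calendar footnote n into one list of conditions for treatment while progression awaits confirmation. If the list uses a change in ECOG, state the visit it is measured from. State whether laboratory worsening counts and whether the clinically-significant qualifier applies. Have the other sections and footnote n refer to that list instead of restating it. Which conditions apply is for the sponsor's clinicians to decide; this review takes no position.

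The cost is amendment wording only. No new data, visits or patients are needed. Decisions already taken can be reviewed for deviations once the sponsor has recorded which text was in force for them.
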